1.4 Primary endpoint

The primary endpoint is the variable "cure" composed by all of the following: a) clinical cure in the test of cure (TOC) (see definition below); b) radiological healing; c) definitive soft tissue coverage at TOC.

The definitions for all the outcomes are specified in the study protocol. The TOC will be performed 12 months after the end of antibiotic therapy prescribed to treat IOM following DAIR, except in patients with delayed infections randomized to the long-treatment regimen (until fracture union) who receive 6 months or more of antibiotic treatment, which will be evaluated 18 months after the start of the study (or randomization).

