4. DATABASE AND MISSING DATA

4.1 Database archive and validation

The study database will be exported from the electronic CRF to SPSS software, and will be maintained at FISEVI files. The Spanish Clinical Research Network (SCReN) team will monitor the data for coherence, missing values and outliers, according to their standard monitoring procedures. All corrections will be performed by the study team together with the external monitoring team before database lock.

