5. STATISTICAL ANALYSIS

5.1 Primary endpoint

The primary endpoint will be collected as a dichotomous variable (yes/no). The primary analysis will be the absolute difference in the proportion of patients reaching the composited primary outcome variable “cure” in the study arms (with one-sided 95% confidence interval) in the ITT population, with the long antibiotic treatment as the reference group. The specific reasons for not reaching overall success (failure, withdrawals, death, etc.) will be specified in both study arms.

A secondary analyses will include subgroups analysis for the primary outcome using the same procedure, and the comparison of the composite variable components (clinical cure, radiological healing and soft tissue coverage) in the PP and CEP, after excluding incorrectly assigned patients.

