5.4 Multivariate analysis

A multivariate analysis will be performed in order to control the potential residual effect of variables other than duration of antibiotic therapy on the primary outcome by logistic regression. Potential confounders will be identified by bivariate analysis of their associations with the primary outcome, considering a p value <0.15 , and will be entered into the multivariate model to check if the effect of the duration of therapy is significantly modified. Expected potential confounders include age, Charlson, delay in DAIR, type and location of fracture, type of osteosynthesis material, microorganism, and antibiotic group. The effect of study sites will be explored by classifying the sites as those with higher and lower cure rates, and including it as a potential confounder.

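### Section 5.4 groups sites by their own cure rate and then uses that group to predict cure, so chance differences between sites can be reported as a site effect

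*SAP*

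**What the plan says.** SAP section 5.4 plans a multivariate analysis of factors other than treatment duration "on the primary outcome by logistic regression". The primary outcome is the yes/no composite *cure* of sections 1.4 and 5.1. Candidate confounders are screened by their bivariate association with cure at p<0.15 and then entered "to check if the effect of the duration of therapy is significantly modified".

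For centres, the section adds: "The effect of study sites will be explored by classifying the sites as those with higher and lower cure rates". The class so formed then goes into the model like the other candidate confounders. The section gives no cut-off between higher and lower, no rule for ties and no source for the rates other than the trial itself.

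The primary analysis in section 5.1 is separate: "The primary analysis will be the absolute difference in the proportion of patients reaching the composited primary outcome variable". It is done in the ITT population and uses no site term.

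**The concern.** Cure is both the dependent variable and the basis for the site covariate. Even if every site had the same underlying cure probability, observed rates would differ by chance. Ranking sites on those rates and splitting them collects the lucky sites on one side and the unlucky ones on the other, so the site term must point towards an effect. The p<0.15 screen gives no protection, because a variable built from the outcome passes it too easily.

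At stake is the site result itself. A reader told that centre was associated with cure could not tell a real difference in surgical or infectious-disease practice from sampling noise. The open cut-off also leaves the split to be chosen after the data are seen.

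**Working it through.** **Inputs.** From the SAP: logistic model for cure, two site classes formed from cure rates, screening at p<0.15. The SAP states no figure for this analysis, so there is none to reproduce. Assumed: 4 to 30 sites, 150 to 300 patients, 80% cure (90% as a variant), median split, 1:1 arms, no site effect and no arm effect. The SAP names no test for site; p<0.05 is used only as a yardstick.

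**Step 1: expected size of the artefact.** Take K equal sites whose rates vary only by chance with standard deviation s. Let m be the mean of the upper half of K ordered standard normal values. The difference between the two group means is 2ms on average and its nominal standard error is s·√(4/K), so

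expected z ≈ 2ms / (2s/√K) = m√K.

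| Sites K | m | Expected z = m√K |
|---|---|---|
| 4 | 0.663 | 1.33 |
| 6 | 0.704 | 1.72 |
| 10 | 0.739 | 2.34 |
| 20 | 0.767 | 3.43 |

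Without any site effect, z should average 0. From 10 sites on, its average already exceeds 1.96. To this approximation neither the sample size nor the cure rate enters, so a larger trial does not cure the problem; the number of sites drives it.

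**Step 2: simulation of the rule.** Model: cure on arm and site group; 3000 trials per setting; 80% cure; 150 or 300 patients allocated to sites at random; Wald test. Percentages are of all trials, with undefined splits counted as not significant.

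| Sites | p<0.05, grouped by cure rate | Passes p<0.15 screen |
|---|---|---|
| 4 | 13–15% | 39–41% |
| 6 | 30–34% | 66–69% |
| 10 | 67–72% | 93–95% |
| 20–30 | 96–100% | 96–100% |
| Control: sites split by enrolment | 4.4–5.5% | 14–16% |

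**Step 3: sensitivity.** A separate simulation used a likelihood-ratio test, equal site sizes, 75 to 300 patients and 70–90% cure. It gave p<0.05 in 13–21% (4 sites), 73–88% (10) and over 99% (20). With unequal sites (300 patients, 80% cure) the figures were 62% (10) and 98.5% (20). The median spurious odds ratio at 300 patients and 80% cure was 1.44, 2.00 and 2.86 for 4, 10 and 20 sites. Step 1 agrees: the standard error of the log odds ratio is √(4/(300×0.8×0.2)) = 0.289, and exp(2.34×0.289) = 1.97 for 10 sites.

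**Step 4: undefined or separated splits.** At 90% cure and 150 patients with 20 / 30 sites, a *greater than median* rule is undefined in 31% / 85% of trials and leaves no failures in the higher group in 21% / 9%. A *median or greater* rule is always defined but separated in 48% / 91%. These rates depend on the tie rule and on how site sizes vary, so no single figure applies.

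**Step 5: the duration effect.** Its false-positive rate was 4.5–5.5% with the site group and 4.2–5.2% without. With a true log odds ratio of −0.5 (300 patients, 10 sites), the median estimate was −0.505 without and −0.508 with the site group.

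**The case against.** The strongest reply concerns purpose. The model exists to check the duration effect, site enters only as a possible confounder, and no claim about site is planned. On that purpose no harm was found (step 5), and the primary analysis never uses the model. This stands, and it is why the point is of low priority. It does not remove the point, because the sentence says that the effect of sites will be explored, and this method cannot do that.

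Second, the SAP does not say in words that the cure rates are those observed in this trial. That is true, but it names no other source, and in-trial rates are the natural reading.

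Third, the size is conditional. With 4 sites about 85% of null trials show nothing at p<0.05, and with 6 about two thirds; a spurious effect becomes the usual result only at about 10 sites or more. This stands and belongs in the conclusion. The range for 10 sites also moves with the test and the balance of site sizes, from 62% to 88% over all settings run.

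Fourth, a random intercept has weak power to detect site differences. It does (figures under the fix), but it does not manufacture them. It was simulated with an intercept only, not alongside arm and the screened covariates.

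**Conclusion.** The concern holds. As written, section 5.4 defines a site covariate from the outcome it then predicts, and following the rule exactly yields chance site effects. The excess over the nominal 5% is roughly threefold with 4 sites (13–15% at 80% cure), and a false signal is nearly certain with 20 or more. The direction and the growth with site count held in every setting run; the exact rates rest on the assumed site count, sample size, cure rate and median split. The consequence is limited to the exploratory site result, so this is a change to consider and no threat to the primary conclusion.

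**What to change.** Replace the site sentence in section 5.4 with:

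> The effect of study site will be explored by adding site as a random intercept to the logistic model; the between-site variance will be reported with a profile-likelihood 95% CI, and an estimate of zero will be reported as no detectable between-site variation, together with the upper confidence limit. Sites will not be grouped by their observed outcome. If the model does not converge, sites will be entered in groups fixed before database lock without reference to outcome (e.g. by number enrolled, small sites pooled).

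Because the section is about the duration effect, it would help to report that effect with and without the site term.

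**Cost.** Three sentences, and these limits:

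- With no site effect (80% cure), the interval excluded zero in 0.4–1.9% of simulated trials, and the variance was estimated at or near zero in 60–76%.
- With an assumed between-site standard deviation of 0.5 on the log-odds scale, the interval excluded zero in only 8–39%, and the estimate was at or near zero in 14–36%. A zero must therefore not be read as proof that sites do not differ.
- The fallback grouping by enrolment detects only differences related to site size.
- Section 4.1 states: "The study database will be exported from the electronic CRF to SPSS software". If the package used gives no profile-likelihood interval, this one model must be run elsewhere.

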5.5 DOOR/RADAR analysis

In order to provide additional information of the different components of the primary endpoint, an analysis with desirability of outcome ranking (DOOR) and response adjusted for duration of antibiotic risk (RADAR) will be performed. First, patients will be classified according to the following ordinal system:

Category	Failure	No bone healing	No soft tissue coverage	Severe adverse event
1	No	No	No	No
2	No	No	No	Yes
3	No	No	Yes	Yes or no
4	No	yes	Yes or no	Yes or no
5	Yes	Yes or no	Yes or no	Yes or no

Second, in case of tie, the duration of total antibiotic duration will be considered; patients with a shorter duration will be given a better category. Finally, the probability of having a worse ranking among patients treated with a short antibiotic regimen than among patient with a long antibiotic regimen will be calculated; the upper bound of the 95% CI of the probability should be $>50\%$ to suggest non-inferiority of short antibiotic regimen.

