1.1 Study hypothesis

The hypothesis of the study is that in IOM of long bone fracture, a short antibiotic treatment is equally effective as a long antibiotic treatment in patients selected for debridement and implant retention. Antibiotic duration can be selected according to the time of diagnosis of IOM as it takes into account the biofilm formation and the state of fracture consolidation:

- a) In patients with early infections (those that occur in the first 2 weeks after implantation of the osteosynthesis material) in whom early debridement is performed, it is possible to shorten the duration of antibiotic treatment to 8 weeks (versus 12 weeks);
- b) In patients with delayed infections (those that occur between 3 and 10 weeks after implantation of the osteosynthesis material) in whom it is not possible to remove the implant due to instability/lack of fracture healing, it is possible, after surgical debridement, to shorten the duration of antibiotic treatment to 12 weeks (vs. maintaining antibiotic treatment until fracture healing or implant removal).
- c) In patients with late infections (those that occur more than 10 weeks after implantation of the osteosynthesis material) healing is not possible until the implant is removed, but when removal is not possible, antibiotic therapy can be maintained until fracture healing or implant removal.

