1.5 Secondary endpoints

- a) **Clinical endpoints:** efficacy of each group of antibiotics, secondary infections, infection recurrence rate (relapses and reinfections), need for new surgeries (debridement, material removal, covering, amputation), reconstructive surgery strategies (bone and soft tissue), functional status (defined as restoration of limb function prior to fracture) and state of health.
- b) **Microbiological endpoints:** Resistance development to antibiotic used during therapy and *C. difficile* infection during therapy and at 30-day.
- c) **Adverse events (AE) and complications:** Adverse events and severity, including death (that is, all-cause mortality).
- d) **Consumption of health resources:** Consumption of health resources will be evaluated for each type of strategy: days of antibiotic treatment, length of hospital stay, readmissions, number and type of surgeries performed.

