4.2 Missing Data

Missing data for key study variables, if any, will be presented and compared across study arms. Missing data for secondary exposure or variables will be considered as such and presented. No imputation of missing data is planned.

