5.2 Secondary endpoints

The secondary endpoints will be collected as dichotomous variables (yes/no) or continuous variables. The ITT, PP and CEP approaches will be used for the analyses of secondary endpoints. The absolute difference with one-side 95% CI proportion will be used for dichotomous variables and absolute difference with one-side 95% CI mean/median (as appropriate) for continuous variables.

5.2.1 Clinical endpoints:

Efficacy of each group of antibiotics used, secondary infections, infection recurrence rate (relapses and reinfections), need for new surgeries (debridement, material removal, covering, amputation), reconstructive surgery strategies (bone

and soft tissue), and functionality of the lower limbs will be reported as proportion. Risk ratios (RRs) and the absolute difference for achieving each endpoint (with 95% CIs), with the long antibiotic treatment arm as the reference group, will be calculated.

Functionality of the upper limbs (Quick-DASH score) and health outcomes (SF-12 or Barthel scores) will be reported as median. The median of each score will be compared between the two treatment groups using parametric or nonparametric tests as appropriate.

5.2.2 Microbiological endpoints: Resistance development to antibiotic used during therapy and *C. difficile* infection during therapy and at 30-day will be reported as proportion. Risk ratios (RRs) and the absolute difference for achieving each endpoint (with 95% CIs), with the long antibiotic treatment arm as the reference group, will be calculated.

5.2.3 Adverse events (AE) and complications: Adverse events and severity, including death (that is, all-cause mortality) will be reported as proportion. Risk ratios (RRs) and the absolute difference for achieving each endpoint (with 95% CIs), with the long antibiotic treatment arm as the reference group, will be calculated.

5.2.4 Consumption of health resources will be evaluated for each type of strategy: days of antibiotic treatment, length of hospital stay, readmissions, and number of surgeries performed will be reported as median. The median of each variable will be compared between the two treatment groups using parametric or nonparametric tests as appropriate.

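### The DOOR/RADAR ranking gives death no rank of its own, and its duration tie-break favours a patient whose antibiotics were cut short by death

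*SAP*

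**What the plan says.** SAP section 5.5 sets up a desirability ranking with five ordered categories, to add information on the components of the primary endpoint. The table has four columns: failure, no bone healing, no soft tissue coverage, and "Severe adverse event". Category 5, the worst, holds every patient with failure. Category 4 holds those without failure whose bone has not healed, category 3 those lacking only coverage, and category 2 those with only a severe adverse event. Patients in the same category are then separated by antibiotic exposure: "in case of tie, the duration of total antibiotic duration will be considered; patients with a shorter duration will be given a better category".

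Death is dealt with elsewhere in the SAP. Section 5.1 names it beside failure: "The specific reasons for not reaching overall success (failure, withdrawals, death, etc.) will be specified in both study arms". Section 5.2.3 puts it under adverse events: "Adverse events and severity, including death (that is, all-cause mortality) will be reported as proportion". Section 1.5 groups it the same way. On definitions, section 1.4 says: "The definitions for all the outcomes are specified in the study protocol". On missing data, section 4.2 says: "No imputation of missing data is planned".

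**The concern.** A desirability ranking is meant to order patients by how good their whole outcome was. Here the least desirable outcome has no place of its own, so its rank depends on which of the four columns a death happens to fill. The SAP does not say which.

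The tie-break adds a second problem. Shorter exposure counts as a benefit because it stands for antibiotics spared. When treatment stops because the patient died, the short duration is a consequence of the bad outcome, yet the rule still credits it.

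What is at stake is the reading of the DOOR/RADAR result: a difference in mortality between arms would be diluted in the one analysis meant to combine benefit and harm.

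**Working it through.** **1. Where a death can fall.** The four yes/no columns give 16 combinations. The table covers all of them: 1, 1, 2, 4 and 8 combinations in categories 1 to 5. A classified death must therefore enter through one of these columns.

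| How the death is coded | Category |
|---|---|
| Failure | 5 |
| Severe adverse event, bone not healed | 4 |
| Severe adverse event, bone healed, no coverage | 3 |
| Severe adverse event, healed and covered | 2 |

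In the last three rows the death ranks above every living patient with failure. In the first it ties with them and wins against any who were treated longer. A patient who dies before bone status is assessed, and is not coded as failure, may have no category at all, since nothing is imputed.

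**2. Size before the tie-break.** The SAP gives no rates, so these are assumptions: 65/8/4/10/13% in categories 1 to 5 in both arms, then 5 percentage points of the short arm moved from category 1 to death, with no deaths in the long arm. Count ties as half. A short-arm patient in a given category ranks worse than a random long-arm patient with probability:

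- category 1: 0.65/2 = 0.325
- category 2: 0.65 + 0.08/2 = 0.690
- category 4: 0.77 + 0.10/2 = 0.820
- category 5: 0.87 + 0.13/2 = 0.935
- separate worst category: 1

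With identical arms, P(short worse) is 0.5. Moving 0.05 from category 1 to category k gives 0.5 + 0.05 × (value for k − 0.325).

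| Deaths placed in | P(short worse) | Share of the shift lost against death ranked worst |
|---|---|---|
| Category 2 | 0.5 + 0.05 × 0.365 = 0.518 | 1 − 0.365/0.675 = 46% |
| Category 4 | 0.5 + 0.05 × 0.495 = 0.525 | 1 − 0.495/0.675 = 27% |
| Category 5 | 0.5 + 0.05 × 0.610 = 0.5305 | 1 − 0.610/0.675 = 10% |
| Own worst rank | 0.5 + 0.05 × 0.675 = 0.534 | – |

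With 10 points of excess deaths the four probabilities are 0.537, 0.550, 0.561 and 0.568.

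A second assumed set (survivors 60/10/5/10/15%, deaths 10% short against 5% long) points the same way: 0.507 and 0.515 with deaths in category 2 and 4, against 0.525 with death ranked worst.

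**3. Size after the tie-break.** Take the early-infection durations in section 1.1, 8 weeks against 12, and assume survivors receive exactly those. The short arm then wins every tie. With no deaths, P(short worse) = (1 − sum of squared shares)/2 = (1 − 0.4574)/2 = 0.2713.

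*Excess deaths in the short arm.* A category 1 patient never ranks worse, so moving 0.05 adds 0.05 × 0.65, 0.77, 0.87 or 1. The results are 0.304 (category 2), 0.310 (category 4), 0.315 (category 5) and 0.321 (worst rank).

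*Excess deaths in the long arm.* This is where truncation itself matters. Suppose these deaths fall in category 5.

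- If the dead patient's duration is counted as 12 weeks, no short-arm patient ranks worse than that patient: 0.2713 + 0.05 × (0 − 0.35) = 0.254. Ranking death worst gives the same figure.
- If death came before week 8, that patient wins the tie against the 13% of the short arm living with failure: 0.2713 + 0.05 × (0.13 − 0.35) = 0.260.

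The shift due to these deaths drops from 0.0175 to 0.011, a loss of 37% that comes from the tie-break alone.

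**The case against.** The strongest objection is that failure probably does include death. Section 5.5 says the ranking informs on the components of the primary endpoint, and its first three columns mirror the three components in section 1.4. Failure then reads naturally as no clinical cure at the test of cure, which a patient who died earlier cannot have reached. Definitions are left to the protocol, which is not at hand; the list of reasons in section 5.1 is not a definition, and reporting a death as an adverse event does not stop it counting as failure.

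This is a fair reading, and it removes the largest effects: on the assumed rates the loss before the tie-break is then about 10%. It does not remove the point. Deaths in category 5 still share a rank with living failures and still win ties on shorter duration, and both rules are fixed in the SAP itself.

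A reader might go further and infer that dead patients will typically sit in the second-best category and also gain from a truncated course. The documents do not support that. Category 2 requires healed bone and covered soft tissue, so it concerns mainly later deaths, when the planned course will usually be complete. A death on treatment will more often precede healing, which points to category 4 or 5.

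Nor can one infer that excess mortality would be hidden in the trial. Sections 5.1 and 5.2.3 report death by arm, the latter with risk ratios, absolute differences and confidence intervals. Finally, in the scenarios worked here every probability after the tie-break stays well below 0.5 wherever death is ranked, so none of them moves the point estimate across 50%.

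**Conclusion.** The point holds under either definition of failure: section 5.5 has no rank for death, and its tie-break credits antibiotic courses that death cut short. The SAP's separate listing of failure and death, and its placing of death under adverse events, suggest categories 2 to 4; the mapping to the primary endpoint suggests category 5. The document does not settle which.

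The result tends to be biased in favour of the arm with more deaths. For 5 points of excess deaths in the short arm, P(short worse) before the tie-break is understated by between 0.003 (0.5305 against 0.534) and 0.016 (0.518 against 0.534). These sizes rest on assumed category rates, on all excess deaths coming from category 1, and, after the tie-break, on exact 8- and 12-week courses. They show direction and order of magnitude, not expected values.

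Severity is low. Only a supplementary analysis is touched; the primary ITT comparison and the mortality reporting stand as planned.

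**What to change.** In section 5.5, add a sixth and worst category, death from any cause before the test of cure, and apply it ahead of the other columns so that every such death is classified even when bone or soft tissue status was never assessed. State that the duration tie-break is not applied among deaths, so that two deaths tie. With death in its own category, a truncated course can no longer outrank a survivor.

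The change is right whichever way the protocol defines failure. It costs SAP wording only: deaths are already a collected endpoint, and sample size, data collection and the primary analysis do not change. It should be made before anyone has seen outcome data by arm.

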5.3 Subgroup analyses

The primary and secondary endpoint will be analysed in the following subgroups:

- Type of infection: early and delayed.
- Type of fracture: open (Gustilo and Anderson classification) or closed.
- Type of osteosynthesis material: endomedullary nail or needle, plates or screws.
- According to the etiology of the infection: infections by different microorganisms, infections by multidrug-resistant microorganisms.

- According to type of patient: comorbidities, elderly, renal insufficiency, gender.

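### The DOOR/RADAR statistic gives tied pairs no half weight, so 50% does not mark equal ranking when full ties remain, as the SAP's two 12-week regimens allow

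*SAP*

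**What the plan says.** SAP section 5.5 places each patient in one of five ordered categories. Its only rule for patients in the same category is this: "in case of tie, the duration of total antibiotic duration will be considered; patients with a shorter duration will be given a better category". It then calculates "the probability of having a worse ranking among patients treated with a short antibiotic regimen than among patient with a long antibiotic regimen". For the decision, "the upper bound of the 95% CI of the probability should be" above 50% to suggest non-inferiority of the short regimen. Nothing is said about pairs with the same category and the same duration, and no stratification is stated for this analysis.

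SAP section 1.1 gives the regimens. In early infection the hypothesis is that one can "shorten the duration of antibiotic treatment to 8 weeks (versus 12 weeks"). In delayed infection it is that one can, after debridement, act "to shorten the duration of antibiotic treatment to 12 weeks (vs. maintaining antibiotic treatment until fracture healing or implant removal"). Section 5.3 lists "Type of infection: early and delayed" as a subgroup factor for the primary and secondary endpoints only.

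**The concern.** A rank comparison of two arms has three outcomes per pair: worse, better or tied. The value 50% stands for equality only if ties are absent or split evenly. Section 5.5 names only the probability of ranking worse, so every pair that stays tied lowers the statistic without being evidence for either arm.

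Full ties are not a remote possibility here. Twelve weeks is the planned duration for one group in each arm, so a pooled comparison sets delayed short-regimen patients against early long-regimen patients with the same planned duration. Section 1.1 does not set those two regimens against each other. At stake is whether the result of this supplementary analysis is read against a reference value that means equal ranking.

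**Working it through.** **1. The reference value.** For any short-by-long pair, P(worse) + P(better) + P(tie) = 1. If the arms rank equally, P(worse) = P(better), so

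P(worse) = (1 − P(tie)) / 2.

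| P(tie) | Strict P(worse) | P(worse) + 0.5 × P(tie) |
|---|---|---|
| 0 | 0.500 | 0.500 |
| 5% | 0.475 | 0.500 |
| 10% | 0.450 | 0.500 |
| 15% | 0.425 | 0.500 |
| 20% | 0.400 | 0.500 |

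The SAP's 50% is reproduced by the strict form only with no ties, and by the half-tie form always.

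**2. Where ties arise.** Regimens are from SAP section 1.1. Full adherence, and more than 12 weeks for the delayed long regimen, are assumed.

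| Short-arm patient | Long-arm patient | Duration |
|---|---|---|
| early, 8 weeks | early, 12 weeks | short arm shorter |
| early, 8 weeks | delayed, over 12 weeks | short arm shorter |
| delayed, 12 weeks | early, 12 weeks | **equal** |
| delayed, 12 weeks | delayed, over 12 weeks | short arm shorter |

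Let e be the share of early infections in each arm. The third row makes up e(1 − e) of all pairs: 0.3 × 0.7 = 21% at e = 0.3 or 0.7, and 0.5 × 0.5 = 25% at e = 0.5. The SAP does not give e.

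**3. Size of the tie share.** Let S be the chance that two patients fall in the same category, that is, the sum of the squared category shares. Then P(tie) = e(1 − e) × S, and the strict statistic is lower than the half-tie form by half of that. The SAP gives no category shares. For assumed shares of 70/5/3/7/15%, S = 0.490 + 0.0025 + 0.0009 + 0.0049 + 0.0225 = 0.521. Values of 0.406 and 0.652 are assumed on either side.

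| S | P(tie), e = 0.3 or 0.7 | Reduction (points) | P(tie), e = 0.5 | Reduction (points) |
|---|---|---|---|---|
| 0.406 | 8.5% | 4.3 | 10.15% | 5.1 |
| 0.521 | 10.9% | 5.5 | 13.0% | 6.5 |
| 0.652 | 13.7% | 6.8 | 16.3% | 8.2 |

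The reduction is thus about 4–8 points. It scales with S: more spread-out shares of 50/10/10/10/20% give S = 0.32 and a reduction of 3.4–4.0 points. It is nil if no two durations coincide.

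**4. Check at equal ranking.** With only categories 1 and 5 in use, assumed long-arm failure of 10–30% and e from 0.3 to 0.7, short-arm failure was solved so that P(worse) = P(better). Ties were then 9.3–12.8% of pairs. Strict P(worse) was 0.436–0.454; with half-ties it was 0.500 throughout.

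**5. Effect on the decision.** Two arms with identical rank distributions were simulated. Assumed inputs were category shares 70/10/5/5/10%, half of each arm at exactly 12 weeks, the rest spread evenly over 8–40 weeks, and a two-sided 95% interval. The strict statistic averaged 0.435.

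| Patients per arm (assumed) | Upper limit below 50%, strict | Upper limit below 50%, half-ties |
|---|---|---|
| 75 | 27% | 3% |
| 150 | 48% | 3% |

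Under the printed rule the complement counts. The upper limit is above 50% in 100 − 27 = 73% and 100 − 48 = 52% of trials with the strict form, against 97% with half-ties. So the missing half-ties make the printed criterion harder to meet and the reverse criterion easier.

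**The case against.** Several points on the other side carry weight.

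- **The sentence may be shorthand.** It describes a rank comparison in prose, and the usual Mann-Whitney-type estimate gives ties half weight. The SAP does not say that residual ties are to be scored in favour of either arm. This stands as a reason to call the point one of definition; but the statistic as literally written omits the half weight.
- **The size is a ceiling for the assumed inputs.** Section 5.2.4 lists days of antibiotic treatment as a variable. If duration is ranked in days, a tie needs two exactly equal totals. The figures also assume that early and delayed infections share one category distribution. This stands.
- **Half-ties do not bring clinically equal arms to 50%.** Under the regimens in step 2, a short-arm patient never loses on duration. With equal category shares of 70/5/3/7/15% and e = 0.5, strict P(worse) is (1 − 0.521) / 2 = 0.24, and adding half of the 13.0% ties gives only about 0.30. Most of the distance from 50% then comes from the duration tie-break, which is the purpose of RADAR. A reader might take equal arms to mean equal clinical outcomes; the argument supports only equal overall ranking.
- **Stratifying already removes the 12-week overlap.** Largely so. But the delayed long regimen has no fixed length, and regimens can be cut short, so equal totals within a stratum remain possible. The half-tie term covers them at no cost.

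Two stronger readings are not supported. One is that the error always favours the short arm: the statistic is always lowered, but with the printed inequality a lower value counts against the short arm. The other is to judge the loss from ties on category alone, which would be far more frequent; section 5.5 always applies the duration tie-break, so that analysis is not planned.

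**Conclusion.** The point holds in a limited form. Read literally, section 5.5 sets a strict probability against 50%, and that is the equal-ranking value only without ties. The SAP's own regimens allow full ties in a pooled comparison. The statistic is then lower by half the tie share: about 4–8 points with S between 0.406 and 0.652, 30–70% early infections and exactly 12 weeks for every such patient, and nothing if no durations coincide. None of these inputs is in the SAP.

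Which way this moves the conclusion depends on the inequality, which needs its own correction: for a probability of ranking worse, evidence in favour of the short regimen would be an upper limit below 50%, not above it. Correcting the inequality alone would leave the tie problem and turn it in favour of the short arm. The matter is minor, because section 5.5 is offered as additional information and the primary ITT analysis in section 5.1 does not depend on it.

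**What to change.** In SAP section 5.5:

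1. Define the statistic as P(short worse) + 0.5 × P(tie), where a tie means the same category and the same total duration, and state the unit in which duration is compared.
2. Compute it separately within early and delayed infection, so that each pair compares regimens that section 1.1 sets against each other. Combine the two with pre-stated weights, for example in proportion to stratum size.
3. Take the confidence interval from this stratified statistic.
4. In the same edit, settle which side of 50% the bound must lie on and what that result is taken to show.

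The cost is a few sentences and a standard stratified rank estimate. No new data are needed.
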